3.6.2 Change of Centres

Due to the ongoing pandemic participants may be required to move hospitals. No IMP will move with the participants and hence dosing will stop. Prophylactic antibiotic use will continue where appropriate.

If participants are moved to a hospital within the study then safety (conmeds, AEs, labs and temperature) and key efficacy data (primary oxygenation endpoint, ordinal scale, respiration data and mortality) will be prioritised.

If participants are moved to a hospital outside the conduct of the study then only key safety data (conmeds, AEs, SAEs) will be collected.

Centre changes will be captured and reported as well as day of transfer. Data collected for participants after transfer to another hospital may not be included in any formal analyses, but will be listed.

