2.4 Determination of sample size

The outcome(s) on which the sample size calculation is based upon, is the primary endpoint measurement of oxygenation, defined as ratio of PaO₂/FiO₂.

The target difference is the difference from baseline measured at the primary endpoint (at day 6 and day 15) between the control and the treated group. Given a sample size of 81 participants, 54 on Zilucoplan® and standard of care and 27 on standard of care there would be >85% power to show a significant difference from standard of care at the 2 sided 5% level if the true underlying treatment difference was an 80 point difference (25% of 320, being the mean at hospital admission) in the PaO₂/FiO₂ ratio. This assumes a standard deviation of 105 and a dropout rate of less than 10%.

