8.2 Statistical analysis of the secondary efficacy endpoint(s)

There are several secondary endpoints that cover each of the secondary objectives and a list is provided in the table listing the secondary endpoints in Section 2.2.1.2. Some of these endpoints are different derivations from the same collected data. In addition, some of the endpoints collected for one objective, may be the inputs to derivations for endpoints for the same objective or for another objective.

Data types for the secondary efficacy endpoints fall into the following main categories: continuous (for example, change from baseline (including the various ordinal categorical endpoints), number of days with 'condition'), ordinal categorical, binary ('responder' Y/N), time to event or duration of event.

Table 8.1 describes the analyses of each secondary endpoint listed in Section 2.2.1.2 and identifies which efficacy objective (2-6) the endpoint is addressing. Brief details of any derivations and analysis methods used are provided. Further details are included in the mock TFL shell document. In the event the data for some of these endpoints indicate that analysis through fitting models is not appropriate, for example too few events for a formal analysis on response or mortality rates, or time to event analyses, the analyses will not be carried out and only listings, figures and summaries provided.

Some patients may withdraw from the study or be transferred to another hospital prior to discharge through medical improvement. If data have been collected from another hospital post discharge from the first hospital, these data will be listed. This will be for variables or derived variables which would have included data from these patients. For example, duration of stay in hospital. However, for variables only including data up to a relative day prior to discharge/transfer from the first hospital, these patients will be included in the analysis/summary

for that period but set as missing for the other periods. Residual plots will be reviewed to determine any influence these participants may have had on the results.

Table 8.1

Endpoint	Derivation	Analysis

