
Objective 2 Incidents of participants reporting each severity rating in 6-point ordinal scale at D1, D6, D15 and D28
	
Percentages for each ordinal score on each day are based on N in each treatment arm on D1. An additional category (score=7) to be created to indicate participants who have withdrawn from the study for any reason or transferred to another hospital. Add label for score category=7 as ‘Withdrawn’. Participants who die (score=1) or are discharged from hospital due to medical improvement (score=6) or are withdrawn (score=7) remain in both the numerator and denominator for these categories on subsequent days by using LOCF for discharge, death and withdrawal. Only use LOCF for participants whose final recorded score is 1, 6 or 7. For the interim, all other subjects whose final recorded score during the period up to 28 days is not equal to 1, 6 or 7, impute a score of 8 for their remaining days (up to D28). This is to indicate the percentage of participants who are still on treatment without imputing what their future values may be.
 
Check that ordinal score matches whether participant has been discharged or has died
	
PROC FREQ to create summary table of actual counts and percentages for each of the 6-points on the ordinal scale on each nominal day (D1, D6, D15 and D28) for each treatment
 
Stacked 100% bar chart indicating a snapshot of counts in each category (color coded for scores 1-7 (including 8 in the interim analyses)) on each relative day by treatment arm. A separate graph for each treatment, placed side by side.
 
For final analysis:
 
Logistic regression for data from specified nominal days (D1, D6, D15 and D28). Fixed effect of Score*Treatment indicating whether the pattern across scores is different between treatments on each day.
 
Note: If D1 is pre-dose and therefore baseline, exclude from table and plot.

Endpoint	Derivation	Analysis

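### Outcomes known after a hospital transfer are not secured for the main analyses, and the ordinal-category table can show a known death as Withdrawn

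*SAP*

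**What the plan says.** SAP 3.6.2 (Change of Centres) expects that the pandemic may force patients to move, and states that dosing stops when they do. If the receiving hospital is in the study, "key efficacy data (primary oxygenation endpoint, ordinal scale, respiration data and mortality) will be prioritised". If it is not, only concomitant medication, AEs and SAEs are collected. The section then adds, for both cases: "Data collected for participants after transfer to another hospital may not be included in any formal analyses". The data are listed, and the day of transfer is reported.

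SAP 8.2, on secondary endpoints, says that data from another hospital are listed. For variables that run up to a day before the move, the patient counts "for that period but set as missing for the other periods". Residual plots are the check on influence.

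In Table 8.1 the ordinal-category endpoint gets an extra score of 7, labelled Withdrawn, for "participants who have withdrawn from the study for any reason or transferred to another hospital". Scores 1, 6 and 7 are carried forward when they are the final recorded score. Time to a 2-point improvement is censored when a patient leaves the first hospital for a reason other than improvement, whereas a death is censored at D15 or D28.

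The 28-day mortality row of Table 8.1 covers every treated participant, derives death within 28 days of randomisation, and names no exclusion for transfer.

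**The concern.** The plan collects outcomes that it may then not use. Three things are at stake.

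- **Known outcomes lost from a secondary endpoint.** A patient who is transferred and then dies can remain in category 7 of the ordinal-category table when the death is known. The same holds for the ordinal score from the Day 28 call.
- **An open choice.** For the primary and mortality analyses, 3.6.2 does not say who decides on inclusion, when, or by what rule. The trial is open-label, so that choice could be made with arm and outcome in view.
- **Assumptions about the gap.** The primary MMRM (SAP 8.1.2) takes missing data as missing at random, and the Kaplan-Meier analyses need non-informative censoring. Both are doubtful if transfer goes with prognosis, whether better or worse.

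**Working it through.** **1. The plan's own figure.** SAP 2.4 states "there would be >85% power to show a significant difference from standard of care at the 2 sided 5% level", with "54 on Zilucoplan® and standard of care and 27 on standard of care", a difference of 80, an SD of 105 and dropout below 10%. By the normal approximation, power = Φ(δ / (σ√(1/n₁ + 1/n₂)) − 1.96).
- 54 v 27: SE = 105 × √(1/54 + 1/27) = 24.75; 80/24.75 = 3.23; power 89.8% (noncentral t: 89.1%).
- 48.6 v 24.3 (10% dropout): SE = 26.09; 80/26.09 = 3.07; power 86.6% (t: 85.7%).

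The stated figure reproduces and is not in dispute. If transferred patients were lost on top of 10% dropout with no usable D6 or D15 value (a worst case, at assumed rates), power would be 84.8% at 5% transferred, 82.9% at 10%, 80.7% at 15% and 78.3% at 20%. If transfers fall within the dropout allowance, nothing changes.

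**2. The passages side by side.**

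| Place in SAP | What happens to a transferred patient |
|---|---|
| 3.6.2 | Later data may be left out of any formal analysis |
| 8.1 (primary) | No rule on transfer |
| 8.2, general text (secondary) | Later data listed; later periods missing |
| Table 8.1, ordinal category | Code 7, carried forward |
| Table 8.1, change from baseline and AUEC | Death carried forward as 1; the change-from-baseline row bars the extra codes |
| Table 8.1, 28-day mortality | No exclusion stated |
| 5.1 (disposition) | Study withdrawal means loss to follow-up or withdrawn consent; transfer is not named; a death at any time counts as completing the study |
| 4.2 | Patients who stop treatment for reasons other than death or discharge may stay on study with data collected |

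A post-transfer death is therefore a completer in 5.1, can be Withdrawn in the category table, and is a death on the face of the mortality row. Protocol 9.2 schedules a Day 28 call for the ordinal score with no exception for transfer, yet a carried-forward 7 would override its answer.

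**3. Size of one misclassified death.** Kept in the denominator as Withdrawn: 1/27 = 3.7 points in the control arm, 1/54 = 1.9 points in Arm A. Set to missing, the change is smaller. For example, 6/27 = 22.2% becomes 5/26 = 19.2%, a fall of 3.0 points.

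**4. Direction of the bias.** The documents give neither a transfer rate nor mortality by transfer, so both are assumed. Let p be true 28-day mortality, t the fraction transferred, and r the mortality ratio of transferred to other patients. Mortality in the others is q = p / (1 − t + t·r). Setting transferred patients to missing estimates q. Keeping them in the denominator as Withdrawn gives (1 − t)q. Deaths after transfer among 81 are 81·t·r·q. With p = 20% and t = 10%:

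| r | Set to missing | Withdrawn in denominator | Deaths after transfer |
|---|---|---|---|
| 0.5 | 21.1% | 18.9% | 0.9 |
| 1 | 20.0% | 18.0% | 1.6 |
| 2 | 18.2% | 16.4% | 2.9 |
| 3 | 16.7% | 15.0% | 4.1 |

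Over p of 10–20%, t of 5–20% and r of 0.5–3, between 0.2 and 6.9 deaths fall after transfer. Setting to missing can push the estimate either way. Leaving known deaths as Withdrawn always understates the death category. These are pooled rates; the effect on the treatment comparison depends on how transfers fall between the arms.

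**The case against.** The case for the plan has real weight.

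- **Primary endpoint.** SAP 8.1 contains no transfer exclusion, and 3.6.2 only permits one. The rule in SAP 3.2.1.3 against mapping data from patients who leave without improvement concerns the discharge-visit value; it does not bar a D6 or D15 blood gas taken at a receiving study hospital. This stands: exclusion here is discretionary.
- **Mortality.** The mortality row excludes nobody for transfer. Mortality is prioritised at study hospitals, and a fatal event is an SAE under protocol 13.1, so a death reported from a non-study hospital would also be known. A reader might infer that the SAP removes post-transfer deaths from 28-day mortality. It does not say so; 3.6.2 and 8.2 leave room for it, and the passages are unreconciled.
- **Code 7.** It belongs to one endpoint and appears as its own category, not merged with survivors. The same cell asks for a check that scores agree with discharge and death, so a programmer might correct a 7 to a 1. This narrows the point to an ambiguity in that table without settling it.
- **Consequence.** Secondary endpoints are exploratory and carry no p-values (SAP 3.1, 4.5). Later data are listed and residual plots reviewed. This limits the harm, but a listing does not correct a percentage.

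The permissive wording of 3.6.2 does not answer the concern, because an undefined choice over known outcomes is itself the weakness.

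**Conclusion.** The point holds for secondary endpoints as stated text, and for the primary and mortality analyses as an unresolved choice. The certain size is 3.7 or 1.9 percentage points per death left as Withdrawn in the 27- or 54-patient arm. Any larger figure rests on assumed transfer rates and risks.

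Two stronger readings are tempting and unsupported. One is that transferred patients are sicker. SAP 3.6.2 gives the pandemic as the only reason for moving, and stable patients could equally be moved; the concern needs only that transfer relates to prognosis in some direction. The other is a definite shift in the primary treatment effect. Suppose 2 of 27 controls are transferred and change by −100 mmHg while the other 25 average +50. The control mean with everyone included is (25 × 50 − 2 × 100)/27 = 38.9, so dropping the two moves it by 11.1 mmHg. But if 4 of 54 in Arm A do the same, that mean is (50 × 50 − 4 × 100)/54 = 38.9 and the difference between arms does not move. These inputs are invented, and raw means are not the MMRM, which can use a D6 value taken before transfer.

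This should be corrected before database lock; it does not undermine the design.

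**What to change.** Amend SAP 3.6.2, 8.2 and Table 8.1 so that they agree:

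1. Outcomes known after transfer enter the main analyses on their nominal days: oxygenation and ordinal score from study hospitals, the Day 28 call score, and deaths from any source, including SAE reports.
2. A known death is scored 1 on the ordinal scale from the day of death and counts in 28-day mortality, whichever hospital it occurred in. The mortality row should say so.
3. Code 7 is kept for withdrawn consent or loss to follow-up, in line with SAP 5.1.
4. Exclusion after transfer becomes a named sensitivity analysis, with transfers reported by arm.
5. SAP 3.6.2 states whether the Day 28 call still takes place for patients in non-study hospitals, since it now limits collection there to safety data.

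The cost is mainly SAP wording, with matching changes to derivations and table shells. For study hospitals the plan already prioritises collecting these data. There are two downsides. Dosing stops at transfer, so the included data contain some off-treatment time. Daily efficacy data will still be missing after moves to non-study hospitals, and the report should say so. Whether patients are analysed as treated or as randomised (SAP 3.5) is a separate matter that this change leaves alone.

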3.7 Coding dictionaries

Adverse events and medical history will be coded using CTCAE V5.0 and the latest available version of the Medical Dictionary for Regulatory Activities (MedDRA®) (Version v 22.0 or higher).

Medications may be coded using the World Health Organization Drug Reference List (WHO-DRL).

Medical procedures will not be coded.

3.8 Changes to protocol-defined analyses

The analysis of the primary endpoint described in the protocol omitted to add that baseline*day would be included as a fixed effect in the Mixed Model Repeated Measures (MMRM) analysis. This is needed in order to account for the fact that values from days closer to baseline are likely to be more correlated than values at days further apart from baseline. This is important if we include D28 and long-term follow-up in some of our analyses.

The primary analyses will be using Nominal Day as the categorical time point, and not strict relative day. This is because whilst the ideal is to take measurements as frequently as possible, the protocol only specifies specific days, which are the primary days for comparing between treatment arms. Therefore, windowing has been incorporated into the derivation of Nominal Day to ensure data that may not have been collected on the specific day of interest, but are within the window, are used. Sensitivity analyses using Relative Day (continuous and/or categorical) will be carried out as described in the relevant sections.

An additional variable will be created to indicate day of discharge and where needed, the results on the day of discharge will be mapped to the appropriate nominal day (Section 3.2.1.3).. This is to match with the sentence in Section 7.1.2 where it describes how to treat data if the day of discharge is prior to D15.

The SAP will not be amended for any changes to planned analyses or any additional analyses that are made after database lock

4 STATISTICAL/ANALYTICAL ISSUES

4.1 Adjustments for covariates

Covariates such as sex, age, BMI (measure of obesity) and race may also be included in the models if by the time of analysis these have been identified as key differentiators in terms of COVID-19 recovery.

Weight may also be used (independently of BMI) as a covariate to explore the impact of weight on results as the usual dosing regimen for Zilucoplan® is to dose by weight.

In addition, the impact on the results of disease severity at baseline may be explored using the 4 middle categories of the 6 point ordinal scale to define disease severity at baseline as a covariate

Where indicated, some secondary endpoints will explore the impact of baseline laboratory values on efficacy endpoints eg Baseline D-Dimers and C5a values.

The addition of the interaction of any baseline covariate with treatment may be explored to identify any evidence to suggest a differential impact on results.

Prior to fitting any model, all data will be explored graphically.

4.2 Handling of dropouts or missing data

The SOE indicates some endpoints are listed as only being collected on the specified days where comparisons between treatments are required, but all clinical and laboratory endpoints will be collected as frequently as possible, preferably daily, whilst in hospital. The primary assessment period is for 28 days post randomization, but some endpoints cannot be collected once a participant has been discharged from hospital e.g. vital signs (including the primary endpoints) and laboratory endpoints.

See Section 5.1 for definitions for Completed Treatment and Completed Study and their complements.

Missing values from participants take 4 forms:

- Missing due to death (no longer 'at risk' of recovery)
- Missing due to hospital discharge prior to end of primary assessment period (on any day up to D28)
- Missing values from the ideal of having daily collection of laboratory and clinical endpoints whilst participants are in hospital
- Missing values due to premature withdrawal from study

How missing data are to be handled is described in the analysis sections for each endpoint.

Participants who discontinue *study treatment* for reasons other than death or hospital discharge (for example, withdraw consent or adverse event, may still continue on study and will have measurements taken, so data from timepoints following discontinuation from *study treatment* will not be missing. These participants/data may be considered differently as part of a sensitivity analysis as they did not receive treatment per protocol.

4.2.1 Safety laboratory data

BLQ values should be set to half the LLOQ and any values above the limit of quantification (ALQ) will be assigned as the value of upper limit of quantification.

4.2.2 Dates and times

A description of how these are to be handled is in Section 13.1.

4.3 Handling of repeated and unscheduled measurements

No measurements are considered as unscheduled as the ideal is to take all clinical and laboratory measurements as frequently as possible.

Repeated measurements are defined as more than 1 measurement at the same timepoint. For example, the same ECG parameters assessed twice due to issues with the first assessment. The use of either the original or repeated measurement performed in any summary or analysis will depend on the reason for repeating the measurement. If repeated measurements are used in any analysis or summary, it will be clearly stated and the reason articulated.

Since the ideal is to take as many measurements as possible, it is possible that more than one measurement will be taken at different times on the same day but is not really considered a repeated measurement under the usual definition. In these cases, the first value taken on any day will be used in any analyses as these should hopefully be taken at the same time on each day and this should avoid any potential bias caused by diurnal variation.

Any listings and graphs of these data over time will include the repeated and/or unscheduled assessments. Sensitivity analyses may be performed using the original and repeated measurements. When more than 1 assessment is available for a specific study moment, these assessments are organized as first the original assessment, assigned to the nominal visit, and then the repeated assessment(s), assigned to unscheduled visits. The date and time of measurement are used to sort the data

4.4 Interim analyses and data monitoring

4.4.1 Interim 1

It is assumed that all data for the primary endpoints will not have been cleaned for this interim analysis.

The analyses of the primary endpoints will be as described in Section 8.1. In addition, the results of the secondary endpoints associated with a 2-point improvement in the 6-point ordinal scale may be analysed, if upon data exploration, formal comparison is meaningful – the percentage of participants who have achieved a sustained (to D15) 2-point improvement or discharge will be compared between treatments and the time to achieving the sustained 2 point improvement or discharge will be estimated. See Section 8.2.1 for a description of the analysis methods.

Safety data will also be reviewed (including adverse events) and presented as described in Sections 10.2 and 10.3 respectively. Mortality will be listed and/or summarized by nominal timepoint and treatment depending on if there is sufficient data to warrant a treatment summary.

There is no plan to stop the study based on results at this stage and no adjustment to control the overall Type 1 error at the final analysis is needed.

4.4.2 Interim 2

Interim 2 analyses will be carried out when all participants have had the opportunity to complete D28 procedures (in clinic or by a phone call if previously discharged) to assess 28 day mortality endpoints and endpoints associated with a 2 point improvement or discharge in the 6-point ordinal scale.

If all data from every participant for the primary objective and 6-point ordinal scale is available *and clean at this time*, this may form the final analysis for the primary objective and key secondary endpoints and be used to guide further research. i.e. there would be no need to wait for the final analysis planned to occur 12-22 weeks post randomization

The analyses of the primary endpoints, 28 day mortality and endpoints associated with a 2 point improvement in the 6-point ordinal score or discharge will be as described in Section 8.1 and Section 8.2.1 respectively.

Safety data will also be reviewed (Adverse events and clinical laboratory parameters) and presented as described in Sections 10.2 and 10.3 respectively.

4.4.3 Safety Data Interim Look

In addition to these interim analyses a Data Safety Monitoring Board is likely to happen after 10 participants have been dosed in Arm A. Additional DSMBs may occur as indicated. UzGhent will manage the DSMB (including the charter) however, the TFLs will be produced by UCB when the 10th active participant is entered in the database with data up to Day 15. The protocol does not state the timeframe of data required, however, it is judged that 15 days of data from 10 active participants will be sufficient to assess safety. AEs, Conmeds, laboratory values, vital signs, exposure will be investigated in Spotfire visualisations and summarized in TFLs if there are sufficient data. To put the safety data in context oxygenation levels, clinical scores, medical history and demography may be considered.

